#### **14.3.7. Reporting Deviations from the Statistical Plan**

Any deviations from the planned analyses will be described and justified in the final clinical trial report.

Study Number: INVEX-CLIN-IIH-301 Protocol	Compound No.: Presendin
	Version: 5.0 for EU countries dated 08Dec2022

## **15. TRIAL ADMINISTRATION**

### **15.1. Regulatory and Ethical Considerations, Including the Informed Consent Process**

Before initiation of a trial site, the Sponsor will obtain approval from the appropriate regulatory agency to conduct the trial in accordance with ICH-GCP and applicable country-specific regulatory requirements.

The trial will be conducted in accordance with all applicable regulatory requirements.

The trial will be conducted in accordance with the EU Clinical Trial Regulation 536/2014, ICH-GCP, all applicable patient privacy requirements and the ethical principles that are outlined in the Declaration of Helsinki 2013, including, but not limited to:

- An IEC/Institutional Review Board review and approval of trial protocol and any subsequent amendments and all ICFs or other information given to the patient
- Patient informed consent
- Investigator reporting requirements

The Sponsor will provide full details of the above procedures, either verbally, in writing, or both.

Written informed consent must be obtained from each patient before participation in the trial. Written informed consent will be collected following a review of the patient's information leaflet by the potential patient and a discussion between the patient and the Investigator or suitably qualified designee.

The Investigator will cooperate with all regulatory inspections and will notify the Sponsor as soon as they are aware of an inspection which may involve this trial. With the exception of statutory regulatory authority inspections, the Sponsor will be consulted in the event of inspection of the clinical site(s) by an outside authority before the Inspectors are permitted access to any of the trial records or the trial areas.

### **15.2. Trial Monitoring**

In accordance with applicable regulations, ICH-GCP, the monitoring plan and the Sponsor's and/or delegate procedures, monitors will contact the site before the start of the trial to review with the site staff the protocol, trial requirements, and their responsibilities to satisfy regulatory, ethical, and the Sponsor's requirements. When reviewing data

Study Number: INVEX-CLIN-IIH-301 Protocol	Compound No.: Presendin
	Version: 5.0 for EU countries dated 08Dec2022

collection procedures, the discussion will include identification, agreement and documentation of data items for which the eCRF will serve as the source document.

The Sponsor and or delegated monitors will perform risk-based monitoring during the conduct of the trial to ensure that:

- The data are authentic, accurate and complete
- The patient’s safety and rights are being protected
- The trial is conducted in accordance with the currently approved protocol and any other trial agreements, ICH-GCP and all applicable regulatory requirements

### **15.2.1. Access to Source Data**

The Investigator and the head of the medical institution (where applicable) agrees to allow the monitor, Sponsor-appointed auditors and regulatory inspectors direct access to all relevant documents.

Information recorded in the eCRF should be supported by corresponding source documentation. Examples of acceptable source documentation include, but are not limited to, hospital records, clinic and office charts, laboratory reports, and recorded data from automated instruments, memoranda, and pharmacy dispensing records.

### **15.2.2. Data Handling and Record Keeping**

Following closure of the trial, the Investigator or head of the medical institution (where applicable) must maintain all site trial records (except for those required by local regulations to be maintained elsewhere) in a safe and secure location. The records must be easily accessible when needed (e.g., for a Sponsor audit or regulatory inspection) and must be available for review in conjunction with assessment of the facility, supporting systems, and relevant site staff.

Where permitted by local laws/regulations or institutional policy, some or all of the records may be maintained in a format other than hard copy (e.g., microfiche, scanned, electronic); however, caution must be exercised before such action is taken. The Investigator must ensure that all reproductions are legible and are a true and accurate copy of the original. In addition, they must meet accessibility and retrieval standards, including regeneration of a hard copy, if required. The Investigator must also ensure that an acceptable back-up of the reproductions exists and that there is an acceptable quality control procedure in place for creating the reproductions.

Study Number: INVEX-CLIN-IIH-301 Protocol	Compound No.: Presendin
	Version: 5.0 for EU countries dated 08Dec2022

The Sponsor will inform the Investigator of the time period for retaining the site records in order to comply with all applicable regulatory requirements. The minimum retention time will meet the strictest standard applicable to a particular site, as dictated by local laws/regulations, the Sponsor SOPs and/or institutional requirements.

The Investigator must notify the Sponsor of any changes in the archival arrangements, including, but not limited to archival of records at an off-site facility or transfer of ownership of the records in the event that the Investigator is no longer associated with the site.

### **15.3. Provision of Trial Results and Information to Investigators**

Where required by applicable regulatory requirements, an Investigator signatory will be identified for the approval of the clinical trial report. The Investigator will be provided reasonable access to statistical tables, figures and relevant reports and will have the opportunity to review the complete trial results at a mutually agreeable location.

The Sponsor will also provide the Investigator with the full summary of the trial results. The Investigator is encouraged to share the summary results with the trial patients, as appropriate.

### **15.4. Publication**

The sponsor will comply with the requirements for publication of study results in a publicly available trials registry such as clinical trials.gov. Results may be published in peer-reviewed journals and presented at scientific meetings. Authorship will be determined by mutual agreement and in line with International Committee of Medical Journal Editors authorship requirements. In accordance with standard editorial and ethical practice, the sponsor supports publication of multicenter studies only in their entirety and not as individual site data. Sponsor will allow the Investigator to review the manuscript before publication by Sponsor. If the Investigator wishes to publish anything related to the trial, then they must provide the Sponsor with the draft publication and allow them no less than 30 days to review the document. The Investigator cannot publish without written authorisation from the Sponsor.

### **15.5. Data Management**

For this trial, patient data will be collected using an eCRF and combined with data provided from other sources in a validated data system. Patient's identifiable data (e.g., name, initials, address etc.) will not be collected in the eCRF or transferred to Invex Therapeutics. Clinical data management will be performed with the objective of removing errors and inconsistencies in the data which would otherwise impact on the

Study Number: INVEX-CLIN-IIH-301 Protocol	Compound No.: Presendin
	Version: 5.0 for EU countries dated 08Dec2022

statistical analysis or the credibility of the Clinical Study Report. Original CRFs will be retained by Invex Therapeutics; the Investigator will also retain a copy.

Management of clinical data will be performed in accordance with the applicable Sponsor standards and data cleaning procedures to ensure the integrity of the data, e.g., removing errors and inconsistencies in the data. Adverse events and concomitant medications terms will be coded using the Medical Dictionary for Regulatory Affairs and World Health Organisation Drug dictionary.

When using electronic trial data handling and/or remote electronic trial data systems, the Sponsor or designee will:

- a. Ensure and document that the electronic data processing system(s) conforms to the Sponsor's established requirements for completeness, accuracy, reliability, and consistent intended performance (i.e., validation)
- b. Maintain SOPs for using these systems
- c. Ensure that the systems are designed to permit data changes in such a way that the data changes are documented and that there is no deletion of entered data (i.e., maintain an audit trail, data trail, edit trail)
- d. Maintain a security system that prevents unauthorised access to the data
- e. Maintain a list of the individuals who are authorised to make data changes
- f. Maintain adequate backup of the data
- g. Safeguard the blinding, if any (e.g., maintain the blinding during data entry and processing)

Training on the use of the electronic data collection system will be provided to all relevant trial site staff.

## **15.6. Independent Adjudication Committee**

The IAC will consist of international medical experts in neurology or ophthalmology who are independent of the Sponsor team.

The role of the IAC will be:

- To support the Investigators with opinions on the eligibility of potential patients
- To provide opinions regarding treatment failure and need for rescue medications required during the trial

Study Number: INVEX-CLIN-IIH-301 Protocol	Compound No.: Presendin
	Version: 5.0 for EU countries dated 08Dec2022

Further details on the composition, activities and responsibilities of the IAC can be found in the IAC charter.

### **15.7. Data Safety Monitoring Committee**

A Data Safety Monitoring Committee (DSMC) consisting of experts in neurology, neuro-ophthalmology and ophthalmology will oversee the conduct of the study and ensure the safety of patients. The role and responsibilities of the DSMC, as well as the data review process are outlined in detail in a separate charter. DSMC reviews of safety data will be planned every 6 months (anticipating the first meeting will occur at approximately 6 months or when 25% of the patients recruited). In addition, unscheduled ad-hoc DSMC meetings will be triggered in case of emerging safety concerns. Based on clinical data reviewed, the DSMC may recommend an amendment to the study protocol or premature termination of the study. Such DSMC recommendations will be submitted to all IRB/IEC and health authorities.

Details on the composition, activities and responsibilities of the DSMC can be found in the DSMC charter.

### **15.8. Insurance, Indemnity and Finance**

The Sponsor maintains appropriate insurance coverage for clinical studies and will follow applicable local compensation laws.

The Sponsor will indemnify all Investigators participating in this trial against future claims by trial patients; the terms of this will be detailed within a separate letter of indemnification. The indemnity will only apply where all trial procedures have been carried out according to this protocol.

The financial aspects of the trial are addressed in a separate agreement.

Study Number: INVEX-CLIN-IIH-301 Protocol	Compound No.: Presendin
	Version: 5.0 for EU countries dated 08Dec2022

## **17. APPENDICES PROVIDED FOR TRIAL INVEX-CLIN-IIH-301**

### **17.1. Appendix 1: LP SOP**

#### Diagnostic lumbar puncture

The diagnostic lumbar puncture (LP) is performed by the site as part of routine care to confirm the diagnosis of Idiopathic Intracranial Hypertension (IIH). This is not a research LP. For the patient to be eligible for the IIH Evolve trial the diagnostic LP must have the opening pressure measured in the lateral decubitus position in line with the guidance below. The LP must be within 4 weeks of commencing screening.

#### Research lumbar puncture

A research LP is performed at the end of the Randomised Period/ Week 24/ Visit 10. This is the primary outcome for the trial. In the 4 weeks prior to visit 10, patients must not have missed more than one dose of trial medication and must have self-administered their final dose within 7 days of visit 10.

Where more than one dose has been missed during the preceding 4 weeks, visit 10 should be delayed. Self-administration of trial medication should continue at 7-day intervals and then visit 10 rescheduled to ensure no more than one dose of the trial medication has been missed in the previous 4 weeks. Visit 10 should be delayed no more than 14 days. We recommend that the LP should be performed after visual assessment.

The LP should be performed by a trained clinician or health care professional according to local standard of care. The only mandatory requirement for the trial is that the measurement of LP opening pressure is conducted as per below.

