- 8 The diagnostic LP will be the baseline LP and must be performed in lateral decubitus position. Patients with ICP <25 cm CSF at diagnosis will be excluded
- 9 Lumbar puncture to be performed after visual assessment. LP to be performed as per Appendix 1. CSF sample from visit 10 LP will be retained for future potential analysis
- 10 Patients will be provided with training on the self-administration of the trial medication. The patient will be asked to self-administer placebo at visit 1 to demonstrate ability to self-inject. Patients who are not comfortable to self-inject will be excluded
- 11 If patients discontinue in the randomised double-blind treatment period they will be encouraged to return for all trial visits up to visit 11. If a patient does not want to return for all visits then they will be asked to return at a minimum for visit 11 procedures for safety follow up
- 12 In the 4 weeks prior to visit 10, patients must not have missed more than one dose of trial medication and must have self-administered their final dose within 7 days of visit 10. Patients will be reminded by the trial site to self-administer trial medication weekly, to continue this until the completion of visit 10 and to bring their trial medication with them at visit 10 for return.  
Where more than one dose has been missed during the preceding 4 weeks, visit 10 should be delayed. Self-administration of trial medication should continue at 7-day intervals and then visit 10 rescheduled to ensure no more than one dose of the trial medication has been missed in the previous 4 weeks. Visit 10 should be delayed no more than 14 days
- 13 Optional unscheduled visit for visual testing (HVF, OCT, LogMAR) for patients in whom there is concern about visual decline or who perform inadequately or where there is technical failure (more than 15% false positive responses or inadequate performance indicated by the Visual Field Reading Centre for HVF; or OCT imaging not of satisfactory quality as determined by the OCT Reading Centre)
- 14 In the event of any abnormal safety assessments identified at end of treatment, e.g., abnormal ECG, abnormal routine laboratory results or ongoing adverse events, this visit may be performed at the clinic to repeat or follow up safety assessments
- 15 Reporting of AEs/SAEs will continue up to the final follow up visit 11

Study Number: INVEX-CLIN-IIH-301 Protocol	Compound No.: Presendin
	Version: 5.0 for EU countries dated 08Dec2022

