- Lumbar puncture (within 7 days of last dose of trial medication)

Study Number: INVEX-CLIN-IIH-301 Protocol	Compound No.: Presendin
	Version: 5.0 for EU countries dated 08Dec2022

- Lumbar puncture to be performed ideally after visual assessments
- Performed in the lateral decubitus position according to LP SOP Appendix 1
- In some cases the lumbar puncture might be conducted using imaging guidance according to the preference of the individual and site. This could be using x-rays, computer tomography or ultrasound guidance.
- If the procedure is not successfully performed it should be re-booked and repeated as soon as possible and the patient should remain on trial medication with the last dose within 7 days of the LP.
- Patient reported outcomes: VFQ-25 & 10-item supp, HIT-6, SF-36 and EQ-5D-5L in diary
- Health Utilisation Form
- Patient global impression of change question
- Laboratory assessments
- Pharmacokinetic blood sampling
- Anti-drug antibodies blood sampling
- Trial medication accountability

Where it is not feasible to conduct all of visit 10 procedures on the same day, these could be split provided visual assessments are performed before the LP and the patient remains on trial medication with the last dose within 7 days of the LP.

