## 12.2. Patient Withdrawal

### 12.2.1. Patient Withdrawal from Trial Treatment

A patient will be withdrawn from treatment for any of the following reasons:

- Withdrawal of consent to continue in the trial. The reason for this will be documented if provided
- The Investigator or Sponsor, for any reason, decides the patient should be withdrawn from the treatment
- Lack of compliance with the trial medication is classified as <75% or >125% of scheduled doses over the course of the trial, excluding supply issues
- Adverse events, which cannot be tolerated by the patient
- Pregnancy during the treatment period
- Retroactive failure to fulfil inclusion/ exclusion criteria (in this clinical drug trial designated phase III), if individual Benefit/Risk does not overrule
- New medical conditions not allowing for continuation of the protocol conform treatment
- Enrolment in any other clinical trial involving an investigational product, or enrolment in any other type of medical research judged not to be scientifically or medically compatible with this study
- If the patient, for any reason, requires treatment with another therapeutic agent that has been demonstrated to be effective for treatment of the study indication
- If the patient, for any reason, requires treatment with a concomitant medication that during this trial should be avoided for reasons of safety and/or efficacy reasons
- Any code breaking/unblinding requested by the investigator
- Protocol-mandated permanent discontinuation of the investigational study treatment

Patients will be encouraged to continue in the trial to the end of the randomised treatment period even if they stop trial medication so that data can be collected for the Intention-To-Treat (ITT) population.

If a patient is withdrawn from treatment during the randomised treatment period, they will be encouraged to return for all trial visits up to visit 10. If a patient does not want to return then at a minimum they should be encouraged to attend for visit 11 procedures as a safety follow-up visit.

Study Number: INVEX-CLIN-IIH-301 Protocol	Compound No.: Presendin
	Version: 5.0 for EU countries dated 08Dec2022

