#### **14.3.1.5. Primary Estimand (Hypothetical assuming no concurrent procedures, irrespective of adherence to treatment)**

The primary estimand is defined as the following for the primary endpoint:

- Treatment difference in ICP measurement between Presendin and placebo at Week 24 for all patients who are randomised and start treatment, regardless of adherence to randomised treatment, where patients did not have medications or procedures likely to materially affect ICP.

The primary estimand for the initial secondary endpoint will be handled similarly to the primary endpoint using the “Hypothetical” approach. The initial secondary endpoint is defined as:

- Treatment difference in PMD between Presendin and placebo over 24-weeks for all patients who are randomised and start treatment, regardless of adherence to randomised treatment, where patients did not have medications or procedures likely to materially affect PMD.

Study Number: INVEX-CLIN-IIH-301 Protocol	Compound No.: Presendin
	Version: 5.0 for EU countries dated 08Dec2022

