#### 14.3.1.6. Secondary Estimand (Hypothetical)

The secondary estimand for the primary endpoint is defined as follows:

- Treatment difference in ICP measurement between Presendin and placebo at Week 24 for all patients who are randomised and start treatment, if all patients adhered to treatment, where patients did not have medications or procedures likely to materially affect ICP.

The secondary estimand for the initial secondary endpoint will be defined as:

- Treatment difference in PMD between Presendin and placebo over 24-weeks for all patients who are randomised and start treatment, if all patients adhered to treatment, where patients did not have medications or procedures likely to materially affect PMD.

All details will be defined in the SAP.

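### The protocol contradicts itself on whether patients who missed doses or stopped trial medication have the week-24 lumbar puncture

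*Protocol*

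**What the plan says.** Section numbers are those of protocol version 5.0.

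**Estimands.** Section 14.3.1.5 defines the primary estimand as the week-24 difference in ICP "for all patients who are randomised and start treatment, regardless of adherence to randomised treatment". Section 14.3.1.6 defines a separate secondary estimand, the difference "if all patients adhered to treatment, where patients did not have medications or procedures likely to materially affect ICP".

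**Condition on visit 10.** Appendix 1 (Research lumbar puncture) states "In the 4 weeks prior to visit 10, patients must not have missed more than one dose of trial medication" and that they "must have self-administered their final dose within 7 days of visit 10". If more than one dose was missed, the visit is put off, weekly dosing goes on, and the visit is rebooked; "Visit 10 should be delayed no more than 14 days". The same rule stands in Table 1 footnote 12, in the visit 10 text of section 6.1 and in section 7. The visit 10 procedure list repeats it on the LP line: "Lumbar puncture (within 7 days of last dose of trial medication"). It also applies to a failed LP that is rebooked and to a visit 10 split over several days. Section 7 lets the 14 days be exceeded in a crisis, but only if dosing is maintained.

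**Follow-up of stoppers.** Section 4.2.2 has patients who cannot tolerate the drug go on attending visits. Section 12.2.1 encourages those withdrawn from treatment to attend through visit 10 so that ITT data are available. It then adds: "If a patient does not want to return then at a minimum they should be encouraged to attend for visit 11 procedures". Table 1 footnote 11 sets the same floor but encourages attendance through visit 11. By section 6.1.6, visit 11 is a telephone call unless a safety finding calls for a clinic visit; neither LP nor perimetry is scheduled.

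**The concern.** An estimand that disregards adherence needs week-24 outcomes from patients who are off drug as well as from those on it. The visit 10 condition works against that in two ways. A patient who lapsed temporarily is put back on drug before the primary measurement. A patient who stopped for good can never meet the condition, although section 12.2.1 wants that patient seen at visit 10.

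Sites are left to choose. One that follows Appendix 1 to the letter would not do the LP in a stopper, or would look for renewed dosing first. One that follows section 12.2.1 would do it. No passage says what happens if the condition still fails after 14 days.

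An LP not taken cannot be recovered by a later analysis plan, so this is a question of data collection that the protocol itself must settle.

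**Working it through.** **1. The plan's own figure.** Section 14.2.1.1 gives about 85% power with 60 completed LPs per arm and 91% with 72, for a difference of 5 cm CSF and week-24 SDs of 9.4 and 10.4. The baseline to week-24 correlation ρ is not stated. I took the 5% level as two-sided.

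- SD = √((9.4² + 10.4²)/2) = 9.91.
- Power = Φ(5 / (9.91·√(1−ρ²)·√(2/n)) − 1.96).
- ρ = 0: 78.9% (n = 60) and 85.7% (n = 72), below the stated figures.
- ρ = 0.35: 83.9% and 89.8%.
- ρ = 0.40: adjusted SD 9.91 × 0.917 = 9.09; 85.4% and 91.0%.

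A simulated ANCOVA at ρ = 0.40 with unequal SDs gave 83.5% and 90.4%. The stated power reproduces at ρ of about 0.35 to 0.40, so the sample size is not in dispute.

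**2. Can the dosing condition be met within 14 days?** Four weekly doses with at least two missed give 6 + 4 + 1 = 11 histories. Count the four doses due 28, 21, 14 and 7 days before the planned visit, and let weekly dosing resume on the planned visit day.

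- Condition met after 7 days: 3 histories.
- Met after 14 days: 7 histories.
- The 4 histories in which both most recent doses were missed need 21 days.
- A permanent stopper never meets it.

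This depends on the counting convention. Suppose the visit-day dose counts and a dose due exactly 28 days earlier does not. At a visit 14 days late, the window then holds the doses of days −7, 0, 7 and 14, with at most one missed, and the condition is met. The protocol does not say which convention applies.

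**3. Possible effect on the estimate.** Let q be the share of the Presendin arm off drug near week 24. The protocol gives no such rate, so q is an assumption.

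- If off-drug patients lose the whole effect, the estimand is 5(1 − q).
- If all their outcomes are replaced by on-drug values (LP after renewed dosing, or missing and imputed from their own arm), the data estimate 5. The gap is 5q: 0.5 cm at q = 10% and 1.0 cm at q = 20%.
- If a fraction f of them is measured off drug or imputed from placebo, the gap is 5q(1 − f). With f = 1/2 it is 0.25 cm and 0.5 cm.
- If half the effect persists off drug and f = 0, the gap is 2.5q, again 0.25 cm and 0.5 cm.

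**4. Power for the estimand as written.** At ρ = 0.40 with no remaining effect off drug, q = 10% gives 4.5 cm and power of 77% (60 per arm) or 84% (72 per arm). q = 20% gives 4.0 cm and 67% or 75%.

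**The case against.** The case for leaving the text alone has substance.

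- **Visit 11 is only a floor.** One might infer that stoppers need only take a telephone call. The documents do not say so: they are encouraged to attend every visit through visit 10, and intolerant patients go on attending.
- **Adherence is not enforced.** The condition looks back 4 weeks and tolerates one missed dose, and no text cancels or discards an LP taken outside it. Appendix 1 also calls only the pressure measurement mandatory. That sentence, however, follows one on who performs the LP and does not clearly cancel the two earlier requirements on dosing.
- **The footnotes may address different groups**, footnote 11 the discontinuers and footnote 12 those still dosing. This reading is possible, but neither footnote states it, and the LP line and the split-visit rule make no such distinction.
- **Imputation helps in part.** Section 14.3.6 uses placebo-like values where data are treated as missing not at random, with discontinuation for an adverse event as its example. Withdrawal of consent is imputed from the randomised arm. A patient who was put back on drug has an observed LP, so nothing is imputed.
- **Brief lapses may not remove the effect.** Section 9.2 puts the time to steady state at 7 to 8 weeks, so total loss of effect is an extreme assumption.

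**Conclusion.** The contradiction stands. The visit 10 passages condition the primary measurement on recent dosing without exempting stoppers, while the primary estimand and the follow-up rules require their data. Followed literally, the condition pulls the observed LPs towards recently dosed patients and can pull the estimate towards the on-treatment effect.

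The size is unknown. The 0.5 cm and 1.0 cm figures are upper bounds for an assumed 10% and 20% off drug; they require complete loss of effect and no placebo-based imputation.

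Three further inferences are tempting but not supported:

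- The visit 10 rules do not amount to measuring the secondary estimand, which supposes adherence to treatment and not just to recent doses.
- Nothing shows that the dosing condition adds to the 40% to 50% of missing LPs in section 14.2.1.1. The protocol attributes those to patients declining an invasive procedure.
- The 4 in 11 histories are patterns, not a share of patients, and depend on how doses at the edge of the window are counted.

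**What to change.** - Reconcile Table 1 footnote 12, the visit 10 text, section 7 and Appendix 1 with sections 4.2.2, 12.2.1 and 14.3.1.5. The result should be that the week-24 LP and visual outcomes are sought from every consenting patient, including those who stopped trial medication.
- Record the date of the last dose at visit 10 and use it for the secondary (adherent) estimand.
- Ask stoppers who will not attend every visit to attend visit 10 as well as the visit 11 safety contact.
- Align footnote 11 (through visit 11) with section 12.2.1 (through visit 10).
- The dosing and delay rule, including what follows if it still fails at 14 days, is for the sponsor to reconcile.

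The cost is protocol wording and site instruction. The estimate may be slightly less favourable, and some off-drug patients would be asked for the LP already scheduled at visit 10.
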